**STUDY SYNOPSIS**

Sponsor	Bernafon AG
Study Title:	A comparative, controlled, clinical investigation and quality control of a new hearing aid in comparison to the currently marketed device.
Short Title / Study ID:	BF001-1611
Protocol Version and Date:	Version 3.0; 02.01.2017
Trial registration:	SNCTP, clinicaltrials.gov
Study category and Rationale	Category C: Medical Device without CE mark
Clinical Phase:	Pre-Market, medical device validation study involving human subjects.
Background and Rationale:	
Benefits of amplification and accessories used with it outweigh any risks in mild to profound hearing impaired subjects. Hearing aids undergo many innovation steps most of them are incremental improvements from already marketed devices. The new devices are expected to perform as well or better than the previous devices.
 
Bernafon conducts clinical investigations in order to test whether new technology provides the same or more benefit than previous Bernafon devices. In addition the aim is to grant quality control prior to product launch according to Bernafon development requirements.
 
The reason for this study is to evaluate a new hearing aid product generation replacing the one on the market. The goal is to evaluate the audiological performance, usability as well as features and functions in comparison to the hearing aid generation already CE marked. Furthermore, it is important to identify unexpected, unwanted behavior from the devices. This clinical investigation is a validation testing and is designed to evaluate the [REDACTED] hearing instrument system. As human subject are involved, this validation test falls under the definition of a clinical investigation. The validation addresses the performance of the device with a new chip, and additionally addresses whether the end user can understand speech as well as with the current device. Evaluating the overall performance of the [REDACTED] hearing instruments is important to verify that the end user is satisfied with the devices and that all User Requirements are fulfilled. All the features available in [REDACTED] with the exception of one new feature, have been validated and are used in devices currently on the market.

Objective(s):	The purpose of this research is to show that the performance of the device is as good as or better than the current device or previous hearing aid generation. Furthermore, speech should not be negatively affected with the addition of the new feature, the usability of the devices (that end users are able to handle the devices) should be as good as the current device, and there should be no artefacts or unwanted noises. Some measurements serve as quality control prior to product launch.

Outcome(s):	
Primary Endpoint:
 

Primary Outcome is the speech intelligibility with the investigational device compared to the current device (using speech tests)

 
Secondary Endpoints:
 

Comparing the subjective performance of the investigational device to the current device (using questionnaires)

Speech intelligibility with the new feature on and off (using speech tests)

Handling/usability of the devices (specified questionnaire)

Subjective preference testing (using interviews)

Procedural safety meaning that there are no unwanted noises or artefacts heard from the devices (as reported by the subjects)

 
Scores from speech tests and questionnaires should be as good as or higher than with previous devices. Handling of the devices should be the same or easier than previous devices. No unexpected, unwanted behaviour from the devices should occur.

Study design:	This is a controlled, open label, comparative clinical investigation conducted monocentric at the premises of Bernafon in Bern, Switzerland.
Inclusion / Exclusion criteria:	
Inclusion Criteria:
 

All classifications of hearing loss (sensorineural, conductive, mixed)

If the hearing loss is conductive or mixed it must be approved for amplification by a physician

All shapes of hearing loss (flat, sloping, reverse slope, notch)

Severity ranging from mild to severe

German speaking

Both genders

Ages 18 and older

Ability and willingness to sign the consent form

 
Exclusion Criteria:
 

Contraindications for amplification

Active ear disease

Inability to follow the procedures of the study due to language problems, psychological disorders, dementia, or other cognitive problems of the participant,

A reduced mobility making them unable to attend weekly study appointments

A reduced ability to describe auditory impressions and the usage of the hearing aids

Uncooperative so that it is not possible to record a valid pure tone audiogram

A strongly reduced dexterity

Central hearing disorders

Bernafon employees

Family members of Bernafon employees

Measurements and procedures:	
Amplification is verified and compared with targets using Real Ear Measured
 
Speech intelligibility tested in quiet or with background noise. Tests used include: Oldenburg Sentence Test (OLSA), Wallenberg and Kollmeier Rhyme Test (WaKo), Oldenburg Logatom Corpus (OLLO). Speech tests are normally set up with speech in the front and noise in the back or at varying degrees around the test client. Some tests such as the OLSA have a varying signal depending on the SNR goal, and others are set to specific speech and noise signal level.
 
Noise acceptance is tested with the Acceptable Noise Level (ANL) Test which uses the most comfortable listening level of the client and then allows the client to adjust the noise until it is too loud.
 
Interviews are conducted with the subjects in order to gather more information about their experience with the hearing aids. The interview is guided with questions but allows for open comments and topics driven by the subjects' comments
 
Preference testing is subjective testing that allows the test person to rate specific settings or devices when listening to the same sound environment.
 
Subjective perception of devices with questionnaires asks the test clients various questions concerning the expectations and benefits of the hearing devices. They can be answered for two different devices or settings and then compared again one another. The questionnaires are the Device Oriented Questionnaire (DOSO), the Abbreviated Profile of Hearing Aid Benefit (APHAB), Speech, Spatial, and Quality Questionnaire (SSQ), and the NASA Task Load Index. Questionnaires designed to address specific topics concerning the new device will be used.
 
Usability and handling is measured with the Practical Hearing Aid Skill Test which asks test clients to perform different handling activities with the devices. Other in-house questionnaires are also used that directly target new hardware or features of the hearing devices.

Study Product / Intervention:	
[REDACTED]
 
The new investigational device will be the [REDACTED] hearing device. The products will have the same features (with the exception of one new) and processing. The differences will be the hardware style and processing chip. Hearing instruments are generally worn for approximately 10 hours every day and removed at night. The test clients will wear the new devices for a time period of 2-3 weeks for each field trial period. In between periods they will wear their current devices.
 
The tested medical devices will be in a stable stage of development. This means that system testing will be completed to ensure correct implementation and safe behavior of the devices before any testing on people is conducted. This also includes the software with which the devices are programmed. The software will be at a stable stage of development

Control Intervention (if applicable):	The reference devices are the subjects' current hearing instruments which are already CE marked, ie. previous technology Bernafon devices. The performance of the new devices will be measured against the previous technology.

Number of Participants with Rationale:	There will be an exploratory analysis of data only. The total number of participants will be approximately 35. For 90% power at the 0.05 significance level, the required sample size is about 24 subjects to detect non-inferiority of the current marketed device with an SD of 2 dB and non-inferiority $\delta$ of 1.3 dB.
Study Duration:	Approximately 4 months The screening of the participants will begin in February of 2017 and the final data collection appointments will occur in May 2017.
Study Schedule:	The first participant is expected to begin in February 2017. The last participant is expected to finish the testing in May 2017.
Investigator(s):	[REDACTED] [REDACTED] [REDACTED] [REDACTED]
Study Centre(s):	The testing will be performed at a single site in [REDACTED] at the [REDACTED].
Statistical Considerations:	The analysis and documentation will be done by the statistician using R (version 3.3.2) a statistical software package. R "stats" package will be used for the confidence interval, non-inferiority, and Wilcoxon tests. Documentation of the analysis will be done with R Studio under R Markdown format. Main outcome: speech reception threshold The paired t-test usually tests that the mean differences are zero. The non-inferiority test compares the difference to a non-zero quantity $-\delta$ .
GCP Statement:	This study will be conducted in compliance with the protocol, the current version of the Declaration of Helsinki, the ICH-GCP or ISO EN 14155 (as far as applicable) as well as all national legal and regulatory requirements.

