## 11.2 Determination of Sample Size

For non-inferiority testing, sample size calculations are the same as those for a 1-tailed test for superiority when the specified  $\delta$  is the same as the superiority population difference to detect (Masha & Sessler, 2011). The sample size calculation follows the recommendation from Chow & Wang (2008), where  $sd$  is the standard deviation,  $\alpha$  the significance level,  $1-\beta$  the power, and  $\delta$  the non-inferiority margin:

$$n = \frac{sd^2 \times (z_{1-\alpha} + z_{1-\beta})^2}{\delta^2}$$

For 90% power at the 0.025 significance level, the required sample size is about 24 subjects to detect non-inferiority of the marketed RMD with an SD of 2 dB and non-inferiority  $\delta$  of 1.3 dB. (Chow & Wang, 2008, p. 52).

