#### 11.4.2 Primary Analysis

Speech Reception Threshold (SRT) will be measured in a single lab test under three test conditions: unaided, control (RMD), and test (IMD) after appropriate training. Test condition order will be randomized using a Latin square design to control any potential order effect. The difference between control and test condition will be compared to the non-inferiority margin to test for non-inferiority. The unaided condition will be used as control of the investigational device benefit if non-inferiority could not be shown.

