#### 11.4.3 Secondary Analyses

- Switching to superiority test will be considered as recommended by the CPMP (2001):

*"If the 95% confidence interval for the treatment effect not only lies entirely above  $-M$  but also above zero then there is evidence of superiority in terms of statistical significance at the 5% level ( $P < 0.05$ ). In this case it is acceptable to calculate the  $P$  value associated with a test of superiority and to evaluate whether this is sufficiently small to reject convincingly the hypothesis of no difference."*

- Hearing loss degree will be added in post hoc analysis as a covariate.

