#### **11.5 Handling of missing data and drop-outs**

For missing data, the PI will contact the involved subject to evaluate the possibility of getting missing data from a questionnaire by post. If a test subject cannot come to the evaluation visit, after exhausting all the possibilities to reschedule a new one, the devices will be sent back per post. If a subject does not want to adhere to the protocol, he can easily switch back to his own device (RMD) and return the IMD.

Data will be immediately removed if the PI has some doubts about the data accuracy (especially about the understanding of the APHAB questionnaire).

Dropouts will not be replaced; therefore, extra subjects over the calculated sample amount will be included from the beginning to ensure enough completed cases with all data.

Analysis will be done on the complete case only.

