3.3 Switching to superiority hypothesis

If the confidence interval for the difference between both devices lies entirely above 0, then "it is acceptable to calculate the P value associated with a test of superiority and to evaluate whether this is sufficiently small to reject convincingly the hypothesis of no difference. There is no multiplicity argument that affects this interpretation because, in statistical terms, it corresponds to a simple closed test procedure. Usually this demonstration of a benefit is sufficient on its own, provided the safety profiles of the new agent and the comparator are similar."

Reference: Committee for Proprietary Medicinal Products (CPMP). (2001). Points to consider on switching between superiority and non-inferiority. British Journal of Clinical Pharmacology, 52(3), 223–228.

4. Required sample size

Reference: Chow S, Shao J, Wang H. 2008. Sample Size Calculations in Clinical Research. 2nd Ed. Chapman & Hall/CRC Biostatistics Series. page 52.

With the following requirements: non-inferiority margin: 1.34, standard deviation: 2 dB, alpha: 0.025, beta: 0.1.

Required sample size:

```
delta <- n.i.m.

sd <- reviewSummary$standev[reviewSummary$study=="16REF"]

alpha <- 0.025

beta <- 0.1
```

out.sample.size <- (sd*(qnorm(1-alpha)+qnorm(1-beta))/delta)^2 ceiling(out.sample.size)

[1] 24

A sample size of 24 will be use to test the non-inferiority hypothesis with a non-inferiority margin of 1.3 dB.

5.References

Alworth, L. N., Plyler, P. N., Reber, M. B., & Johnstone, P. M. (2010). The effects of receiver placement on probe microphone, performance, and subjective measures with open canal hearing instruments. Journal of the American Academy of Audiology, 21(2010), 249–266. http://doi.org/10.3766/jaaa.21.4.4

Committee for Proprietary Medicinal Products (CPMP) (2001). Points to consider on switching between superiority and non-inferiority. British Journal of Clinical Pharmacology, 52(3), 223–228.

D'Agostino, R. B., Massaro, J. M., & Sullivan, L. M. (2003). Non-inferiority trials: design concepts and issues - the encounters of academic consultants in statistics. Statistics in Medicine, 22(2), 169–86. http://doi.org/10.1002/sim.1425

Del Re, A. C. (2015). A Practical Tutorial on Conducting Meta-Analysis in R. The Quantitative Methods for Psychology, 11 (1), 37-50.

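### The significance level is 0.05 in the synopsis but 0.025 in 11.2 and the SAP, and 24 completers give 86% rather than 90% power for the planned paired t-test at 1.3 dB; 27 are needed

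*Protocol*

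**What the plan says.** The synopsis, under Number of Participants with Rationale, says "For 90% power at the 0.05 significance level, the required sample size is about 24 subjects", with an SD of 2 dB and a margin of 1.3 dB, and plans about 35 participants. It does not say whether 0.05 is one- or two-sided.

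Protocol 11.2 describes the calculation as one-tailed, prints a normal-approximation formula with z at 1 − α, and says "For 90% power at the 0.025 significance level, the required sample size is about 24 subjects", with the same SD and margin.

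SAP section 4 lists its inputs as "non-inferiority margin: 1.34, standard deviation: 2 dB, alpha: 0.025, beta: 0.1" and obtains 24. It then concludes: "A sample size of 24 will be use to test the non-inferiority hypothesis with a non-inferiority margin of 1.3 dB".

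Protocol 11.4.2 gives the primary comparison as "The difference between control and test condition will be compared to the non-inferiority margin to test for non-inferiority", without a level or a confidence limit. The only confidence level attached to the device comparison is in 11.4.3, on switching to superiority: "If the 95% confidence interval for the treatment effect not only lies entirely above". The planned test is a paired t-test against −margin (protocol 11.4, SAP 3.2).

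Section 11.5 does not replace dropouts, analyses complete cases only, and says that "extra subjects over the calculated sample amount will be included from the beginning to ensure enough completed cases with all data".

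**The concern.** There are two points.

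**Level.** The same 24 subjects, power, SD and margin appear with two different values of α. They agree only if the synopsis means two-sided 0.05, which it does not say. Since 11.4.2 gives no level either, the decision rule for the primary test has to be inferred from other sections.

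**Size.** The SAP calculates with one margin and adopts another, and the formula is not the one that matches the planned test. Both differences make 24 look better than it is. Section 11.5 takes the calculated number as the base above which extra subjects are added, so 24 acts as the floor for complete cases. A team ending with 24 completers would believe it had the planned 90% power.

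**Working it through.** **Inputs.** SD 2 dB (synopsis, 11.2, SAP 4). Power 90%. Adopted margin 1.3 dB (11.1, 11.2, SAP 3.1). True difference 0, the value implied by the formula, which has no term for a true difference. Quantiles: z(0.975) = 1.960, z(0.95) = 1.645, z(0.90) = 1.282.

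**1. Reproduce the 24.** SAP 3.1 computes the margin as 2 − 1.31/2 = 1.345 dB, rounds it to 1.3 for display, and passes the unrounded value (printed as 1.34 in section 4) to the sample-size code.

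n = [SD × (z(1−α) + z(1−β)) / δ]² = [2 × 3.2415 / 1.345]² = 23.23, rounded up to **24**. Using 1.34 gives 23.41, also 24. The SAP figure reproduces.

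**2. Same formula, adopted margin.** With δ = 1.3: [2 × 3.2415 / 1.3]² = 24.87, rounded up to **25**. So the formula in 11.2, with the inputs printed in 11.2, does not return 24.

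**3. Same formula, synopsis level read literally.** With α = 0.05 and δ = 1.3: [2 × 2.9264 / 1.3]² = 20.27, rounded up to **21**. The 24 therefore fits 0.05 only if it is two-sided.

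**4. The planned test.** Power of the one-sided paired t-test comes from the non-central t distribution with n − 1 degrees of freedom and non-centrality δ/SD × √n. At n = 24 and δ = 1.3 the non-centrality is 0.65 × 4.899 = 3.184 and the critical value is 2.069. Power is **86.2%**. A simulation of 400,000 trials gave 86.3%.

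| Completers | Paired t-test power, 1.3 dB, one-sided 0.025 |
|---|---|
| 24 | 86.2% |
| 25 | 87.6% |
| 26 | 89.0% |
| 27 | 90.2% |
| 35 | 96.2% |

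**5. Where the shortfall at 24 comes from.**

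| Method and margin | Power at 24 |
|---|---|
| Normal approximation, 1.345 dB (as in the SAP) | 90.9% |
| Normal approximation, 1.3 dB | 89.0% |
| Paired t-test, 1.345 dB | 88.4% |
| Paired t-test, 1.3 dB (as planned) | 86.2% |

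Rounding the margin down costs about 2 percentage points and replacing z by t about 2.5 to 3. For comparison, 24 completers at one-sided 0.05 would have 92.6% power with the paired t-test at 1.3 dB, so the level matters to the claim.

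**6. Losses that can be absorbed from 35.** With a floor of 24: 35 − 24 = 11 (31%). With a floor of 27: 35 − 27 = 8 (23%).

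**The case against.** The strongest reply is that little turns on this. The 24 is not a slip: it follows exactly from the SAP's inputs, the protocol calls it approximate, and the step from 25 to 27 replaces a declared and cited approximation by a more exact method. About 35 are to be enrolled, 11.3 plans one analysis after all recruited subjects finish, and nothing stops the trial at 24. Power drops below 90% only if 9 or more of 35 (26%) are lost. All this is right, and it limits the weight of the point. It does not make the stated power correct for the test and margin the plan adopts, and SAP 4 commits to 24 without a qualifier.

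On the level, one-sided 0.025 and two-sided 0.05 are the same test here, and 11.2, the one-sided hypotheses, the SAP code and the 95% interval in 11.4.3 all point to it. That is probably what the synopsis means. The remedy is to write it, and to write it in 11.4.2 as well.

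The third reply is that 27 is no firmer than its SD. The 2 dB comes from unaided-minus-aided data in the internal 2016 reference test, and the documents give no SD for the difference between the two devices. With the paired t-test at 1.3 dB, an SD of 1.85 needs 24 completers, 1.9 needs 25, 2.2 needs 33 and 2.3 needs 35; the range of SDs in the SAP table, 1.4 to 2.3, gives 15 to 35. This stands as a caveat, and it applies to 24 just as much as to 27. The number also depends on the margin and must be recalculated if the margin changes.

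**Conclusion.** The concern holds. The synopsis states the level differently from 11.2 and SAP 4 and omits the sidedness, and 11.4.2 gives no level. With the adopted margin of 1.3 dB and the planned paired t-test, 24 completers have 86.2% power, not 90%; 27 are needed. This rests on an SD of 2 dB for the paired device difference (an assumption), a true difference of 0 and one-sided 0.025. The consequence is moderate: the stated level and completer target should be corrected, but enrolment of about 35 is sufficient under the same assumptions.

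**What to change.** - **Level.** In the synopsis, 11.2 and 11.4.2, state: one-sided 0.025, that is, non-inferiority is concluded if the lower limit of the two-sided 95% confidence interval of C − T lies above −margin.
- **Size.** In the synopsis, 11.2 and SAP 4, state: paired t-test, margin 1.3 dB, SD 2 dB, true difference 0; 27 completers give 90% power, 24 give 86% and 35 give 96%. Use the same margin in the calculation as in the test, and recalculate if the margin changes.
- **Floor.** In 11.5, name 27 as the completer target.
- **Caveat.** Note beside the size that the 2 dB SD comes from unaided-minus-aided data and is assumed for the device comparison.

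The cost is wording in five places. No participants are added; the losses that can be absorbed from 35 fall from 11 to 8.

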## STUDY SUMMARY IN LOCAL LANGUAGE

This study is designed to investigate the performance of the investigational hearing aid in the laboratory and in daily life. In addition, the performance of the hearing aid will be compared with Bernafon aids that are already sold on the market. The hearing aids will be adjusted to the user's requirements. Subjective and objective evaluations will be made using speech testing, questionnaires, interviews, and usability testing. By using data obtained from the trial, the aim is to show that the performance of the investigational hearing aids is the same as or better than the current CE marked hearing aid.

Language of subjects (German):

Diese Studie wurde konzipiert/erstellt, um die Leistung des Hörgeräts sowohl unter Labor- als auch unter Alltagsbedingungen zu untersuchen. Zusätzlich werden die Leistungsdaten des Hörgeräts mit den von Bernafon bereits auf dem Markt verfügbaren zu vergleichen.

Die Hörgeräte werden gemäss der Benutzeranforderungen angepasst. Es werden sowohl subjektive als auch objektive Evaluierungen durchgeführt mittels Sprachtests, Fragebögen und Usability-Tests. Mit der Verwendung der durch die Studie erhobenen Daten wird beabsichtigt aufzeigen zu können, dass der Nutzen des untersuchenden Hörgeräts identisch oder höher ist als die gegenwärtig CE gekennzeichneten Hörgeräte. Ein weiteres Ziel ist es, die Anpassung des Hörgeräts zu verbessern, um den Nutzen für Menschen mit Gehörschaden weiter zu steigern.

## ABBREVIATIONS

Provide a list of abbreviations used on the protocol - to be completed

AE	Adverse Event
CA	Competent Authority (e.g. Swissmedic)
CEC	Competent Ethics Committee
CRF	Case Report Form
ClinO	Ordinance on Clinical Trials in Human Research ( in German: KlinV, in French: OClin )
eCRF	Electronic Case Report Form
CTCAE	Common terminology criteria for adverse events
DSUR	Development safety update report
GCP	Good Clinical Practice
IB	Investigator's Brochure
Ho	Null hypothesis
H1	Alternative hypothesis
HFG	Humanforschungsgesetz (Law on human research)
HMG	Heilmittelgesetz
HRA	Federal Act on Research involving Human Beings
IMD	Investigational Medical Device
IIT	Investigator-initiated Trial
ISO	International Organisation for Standardisation
ITT	Intention to treat
KlinV	Verordnung über klinische Versuche in der Humanforschung ( in English: ClinO, in French OClin )
LPTh	Loi sur les produits thérapeutiques
LRH	Loi fédérale relative à la recherche sur l'être humain
MD	Medical Device
OClin	Ordonnance sur les essais cliniques dans le cadre de la recherche sur l'être humain ( in German : KlinV, in English : ClinO )
PI	Principal Investigator
RMD	Reference Medical Device
SDV	Source Data Verification
SOP	Standard Operating Procedure
SPC	Summary of product characteristics
SUSAR	Suspected Unexpected Serious Adverse Reaction
TMF	Trial Master File

